For these reasons, we seek to develop and test a social media based intervention for cannabis use among EAs, delivered by health coaches who will be similar age or slightly

Full Study Title: Harnessing social media to reduce cannabis use among adolescents and emerging adults in an urban emergency department

older peers (i.e. clinical practicum students, bachelor's level psychology students, master's level public health and social work students). The guiding framework for this intervention can be found in Figure 1.

Objective

The specific aims of this clinical trial is to:

Conduct a randomized clinical trial of the SnapCoach intervention, where we will examine feasibility and acceptability of the SnapCoach Intervention as our primary outcome measures. As exploratory, other outcomes we will examine the preliminary efficacy of SnapCoach (vs. usual care control with attention-placebo; N=approximately 50 per group) on cannabis use (quantity, frequency) and consequences.

We will conduct a randomized clinical trial (RCT), to examine the feasibility, acceptability, and initial efficacy of the SnapCoach intervention. Our goal is to recruit N = 100 participants (as our target N) meeting eligibility criteria, who will complete baseline measures, and be randomized to receive the SnapCoach intervention or a control condition. They will participate in the 4-week intervention/control condition, with a post-test administered at 1-month post-baseline (i.e., end of 4-week intervention period) and a follow-up assessment of outcomes at 3-months post-baseline.

Primary outcomes are feasibility and acceptability of the Snapcoach intervention. Other exploratory outcomes include measures of cannabis quantity and frequency and consequences measured at the 3-month follow-up, examining the effect of the intervention on other substance use (alcohol, other drugs), analyses of moderators and mediators (e.g., sex, cannabis use motives), identification of the most engaging intervention content, dose-response analyses, and measurement of intervention delivery costs.

Aim 2 Methods:

Enrollment

Target enrollment is 100 emerging adults (approximately 50% males and 50% females) between the ages of 18-25, in a 2-arm pilot RCT of SnapCoach compared to an enhanced usual care (EUC) with attention placebo for EAs with weekly cannabis use.

Recruitment Procedures

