Demographics: Age, Sex, Race, Ethnicity (adapted from national surveys, e.g., the Youth Risk Behavior Survey ³⁹)	S
Demographics: Gender identity, Sexual Orientation, School Status, Employment, Living Situation, Children, Marital Status, Pregnancy (adapted from national surveys, e.g., the Youth Risk Behavior Survey ³⁹)	B,3M
Demographic: Parents and Personal Income ^{86,87}	B
Service Utilization: ER and Urgent Care ^{86,87}	B,3M
1-minute delay discounting task ⁸⁴	S,1M,3M
Snapchat involvement (modified) ^{22,40,41,42}	S
Comprehensive Marijuana Motives (modified) ⁴³	B,3M
Perceived risk of cannabis (modified for different cannabis modalities) ⁴⁴	S,1M,3M
Importance, Self-Efficacy, Intention Rulers ^{45,46}	B,I,1M,3M
Cannabis acquisition, strain, and medical marijuana ^{47,48,49,50,51,74}	
Cannabis acquisition	B,1M,3M
Preferred Marijuana Strain	B
Medical Marijuana	S,3M
NIDA modified ASSIST ^{65,66,85}	S,3M
Alcohol use frequency (AUDIT-C) ⁷³	S,3M
Tobacco and Nicotine use (modified) ⁶⁵	S,1M,3M
Mental health: Patient Health Questionnaire-2; Generalized Anxiety Disorder-2 ^{52,53,54,55,56,57,58,59,60,61}	B,1M,3M
Protective Behavioral Strategies for Marijuana (modified) ⁷⁷	B,3M
Gun Carriage ^{75,76}	B
Hope ⁷⁸	B,1M,3M

Peer/Social Influences
	
Cannabis online norms and exposure ^{64,41}	B,1M,3M

Exploratory Outcomes
	

Full Study Title: Harnessing social media to reduce cannabis use among adolescents and emerging adults in an urban emergency department

Cannabis use method, frequency and quantity ⁷⁴ (modified) Smoke, Vape, and Dab (frequency, quantity) Drink and all methods combined (frequency, quantity) Number of days all methods combined Number of days vaped	S,3M B,3M B,1M,3M 1M
Cannabis and Other Drug Use Frequency, Alcohol Quantity/Frequency(TLFB) ^{67,68,69,70}	B,3M
Brief Marijuana Adolescent Consequences Questionnaire (modified) ⁷¹	B,3M
Impaired driving (modified) ⁷²	B,3M
Primary Outcomes: Feasibility/Acceptability of Intervention	
Brief Intervention acceptability ratings (created for this study)	I
Snapchat acceptability ratings (created for this study)	1M
Brief intervention feasibility (e.g., % of participants completing brief intervention)	I
Snapchat health coaching feasibility (e.g., % of participants who complete process of adding health coach on Snapchat, % of participants who reply to at least 1 Snapchat message)	I,1M

Data Management and Analysis

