Randomized participants will be included in intent-to-treat analyses, regardless of group engagement. By design, groups will be balanced based on sex, age, and more than once a day cannabis use, using urn randomization in blocks of 4; we will validate randomization by evaluating covariate balance between groups. If significant differences that could be confounding emerge, we will adjust for those variables or conduct stratified analyses.

Analyses pertaining to primary outcomes of feasibility and acceptability of the intervention are primarily descriptive in nature (e.g., % completing the assigned intervention condition, % engaging in Snapchat messaging, ratings of intervention satisfaction).

For analyses of other exploratory outcomes pertaining to cannabis use, alcohol, and drug use, we will first compare groups on cannabis quantity and frequency using basic two sample comparisons, operating on the pre-post differences (e.g., 3M-Baseline) to test for treatment effects. Our first choice will be a two-sample *t*-test to compare the pre-post differences between groups; considering non-parametric alternatives as needed. To assess changes in the dependent measures (e.g., use days, quantity, cannabis consequences) over follow-up we will use generalized linear mixed models (GLMMs) to jointly study the 1M and 3M outcomes, where possible, while adjusting for correlations between data points (e.g. repeated measurements on individuals). While adjustment for the baseline measurement is important for guarding against regression to the mean in RCTs¹⁹⁵, using this baseline adjustment at every time point can result

Full Study Title: Harnessing social media to reduce cannabis use among adolescents and emerging adults in an urban emergency department

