Aim 2: The sample size is $N = 100$ (approximately 50 per group). For our primary analytic goal – examining feasibility and acceptability this is acceptable. With regard to other exploratory analyses estimating treatment effects – we are comparing two groups of size $n = 50$. Assuming no substantial covariate adjustment is needed, testing the significance of the treatment effect at a single time point will be equivalent to the comparison of two means, for which we use Cohen's D (0.2: small, 0.5: medium, 0.8: large) as an effect size. Under the expected sample size, we will have sufficient power ($>80\%$) to detect effects on both our cannabis and other substance use outcomes if $d > 0.56$, a medium effect size. Although the required effect size is non-negligible, the proposed pilot will provide the critical data necessary to inform the power analyses for a subsequent efficacy trial. While effect sizes from pilot studies

Full Study Title: Harnessing social media to reduce cannabis use among adolescents and emerging adults in an urban emergency department

can have large standard errors and be unstable,²⁰² we can use these pilot data to estimate point estimates and confidence intervals for our treatment effect sizes using the R package MBESS²⁰³.

Data Confidentiality Plans

Our study team will take the following steps to minimize potential confidentiality breaches. As done in prior research and deemed HIPAA compliant by the IRBs at University of Michigan (UM) and HMC by use of a waiver of HIPAA authorization, minimal clinical data will be collected on ED patients who refuse to participate in the screening survey, and on ED patients who the research assistants fail to approach or contact (for remote recruitment). ED-based intervention, TLFB assessment sessions and any phone interviews (e.g., in the event a person cannot attend a follow-up in person, or during remote recruitment, we can administer the TLFB by phone) will be audio-recorded and will be destroyed after the conclusion of the study.

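### The power statement treats all 100 recruited participants as analysed at 3 months, so any loss to follow-up takes power at d = 0.56 below the claimed 80%

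*Combined protocol and SAP*

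**What the plan says.** The Objective section fixes the number to be enrolled: "Our goal is to recruit N = 100 participants (as our target N) meeting eligibility criteria". These participants are then randomised to two arms, and the cannabis outcomes are assessed 3 months after baseline.

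Power calculation and sample size carries the same 100 into the power calculation: "we are comparing two groups of size $n = 50". It argues that "testing the significance of the treatment effect at a single time point will be equivalent to the comparison of two means", measures the effect by Cohen's d, and concludes that "we will have sufficient power ($>80\%$) to detect effects on both our cannabis and other substance use outcomes if $d > 0.56". Neither the significance level nor the sidedness is stated.

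Under Data Management and Analysis, the first comparison is a two-sample t-test "operating on the pre-post differences (e.g., 3M-Baseline) to test for treatment effects". A mixed model follows, intended "to jointly study the 1M and 3M outcomes, where possible". Nowhere does the document give an expected retention, an inflation for loss, or an imputation method for missing 3-month outcomes. Study Procedures describes reminders, payments and a choice of follow-up modes, but attaches no expected rate to them.

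**The concern.** The number recruited and the number analysed are the same figure. A t-test on the change from baseline to 3 months can use only people who have a 3-month value. If 0.56 is the effect detectable with exactly 50 analysed per arm, the plan has no slack and the stated power is a best case presented as the expected one.

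This is the plan's only power figure. The same section says the pilot is meant to inform the power analysis of a later efficacy trial, so a reader should be able to see what effect this sample can realistically detect.

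**Working it through.** **Inputs.** From the document: 50 per arm, d = 0.56, 80% power, a comparison of two means without covariate adjustment. Assumed: two-sided 5%, equal loss in both arms, d in SDs of the 3-month-minus-baseline change (the variable the t-test uses), and loss of 10%, 20% or 30% for illustration.

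**Step 1: reproduce the plan's figure.** Normal approximation:

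- Detectable d = (1.960 + 0.842) × √(2/n). With n = 50: 2.802 × 0.200 = 0.560.
- Power = Φ(d√(n/2) − 1.960). With n = 50 and d = 0.56: Φ(2.80 − 1.96) = Φ(0.84) = 80.0%.

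The noncentral t calculation gives 79.2% power and a detectable d of 0.566. So 0.56 is the 80% boundary at 50 analysed per arm, within rounding. A one-sided 5% test at 50 per arm would give a detectable d of 0.50, which does not match. Two-sided 5% with no loss is the reading that fits the plan's own n and d.

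**Step 2: reduce the number analysed.** Analysed per arm = 50 × (1 − loss). Same formulas, t-test first and normal approximation in brackets:

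| Loss | Analysed per arm | Power at d = 0.56 | Detectable d at 80% power |
|---|---|---|---|
| 0% | 50 | 79.2% (80.0%) | 0.566 (0.560) |
| 10% | 45 | 74.8% (75.7%) | 0.60 (0.59) |
| 20% | 40 | 69.6% (70.7%) | 0.63 (0.63) |
| 30% | 35 | 63.7% (64.9%) | 0.68 (0.67) |

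Like for like, the cost of loss alone is 4.4, 9.6 and 15.5 points with the t-test, or 4.3, 9.3 and 15.1 with the normal approximation. The remaining point or so is the difference between the two methods. Losing one person per arm (49 against 49) gives 78.35% (79.2%).

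**Step 3: can the mixed model recover those lost?** Only where a 1-month value exists. Among the exploratory outcomes in Table 1, that means the days-of-use items: "Number of days all methods combined" at baseline, 1 and 3 months, and days vaped at 1 month. For the first of these, someone seen at 1 month but not at 3 can still contribute. The Timeline Follow-Back row and the consequences questionnaire are listed at baseline and 3 months only, and the cannabis quantity items have no 1-month value. For these outcomes the mixed model gains nothing from a participant lost by 3 months. The timing codes for the method, frequency and quantity items share one table cell and are read here in the order listed. The other two rows are unambiguous.

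**The case against.** **The calculation is openly conditional on 50 per group and is correct on that condition.** This stands. The fault is an unstated assumption of complete follow-up, not a slip in the sum.

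**The scale of d is a choice.** This is the strongest point. The power section speaks of two means at one time point and does not say whether d is in SDs of the outcome or of the change. If it is in SDs of the outcome, power for the change-score test depends on the baseline to 3-month correlation r, which the document does not give. The SD of the change is then √(2(1 − r)) times the outcome SD. With 40 analysed per arm, d = 0.56 on the outcome scale gives about 62% power at r = 0.4, 70% at r = 0.5, 79% at r = 0.6 and 89% at r = 0.7. Baseline adjustment in the mixed model could do better still. On that scale, power could therefore end up above or below the stated figure. But the plan claims no gain from baseline information, and on either scale loss lowers power relative to full follow-up.

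**The significance level is not stated.** A one-sided 5% test would need only 40 or 41 per arm at d = 0.56, leaving room for 18% to 20% loss. That reading does not fit the stated n of 50 together with 0.56.

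**Going strictly above 80% at exactly 0.56 needs 51 (normal) or 52 (t-test) per arm.** This reflects two-decimal rounding and t versus normal, so it is not counted here as a shortfall.

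**Intention-to-treat covers everyone randomised.** It does, but it creates no 3-month value for a person who was not assessed, and no imputation is planned.

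**The consequence is small.** This also stands. The primary outcomes are descriptive, the section justifies 100 on feasibility grounds, concedes that the required effect is not negligible, warns that pilot effect sizes are unstable and plans confidence intervals.

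**Conclusion.** The concern holds, as a minor point. The claim of more than 80% power at d above 0.56 describes complete 3-month follow-up of everyone recruited. For the planned first-choice test, with d in SDs of the change and a two-sided 5% level, any loss takes power at 0.56 below 80%. An assumed 10% to 30% loss leaves 74.8% to 63.7% power and a detectable d of 0.60 to 0.68. The size depends on a loss rate that the document does not supply; the direction does not. No trial decision turns on it.

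**What to change.** Keep the 100 participants and all the analyses. Replace the power sentence with one that states the test level, the scale of d and the retention expected, for example:

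> With [__]% of 100 participants expected to be analysed at 3 months, a two-sided 5% two-sample t-test has 80% power for d of about [0.60 at 90%, 0.63 at 80%, 0.68 at 70%], where d is the group difference in mean change from baseline to 3 months divided by the SD of that change.

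The team should fill in its own retention figure. If it prefers d in SDs of the outcome, it should say so and give the baseline to 3-month correlation it assumes.

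The cost is one sentence and a slightly less favourable detectable effect for the exploratory outcomes. No extra participants are needed.
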